7.2 NULL AND ALTERNATIVE HYPOTHESES

The analyses in this trial are descriptive and exploratory. No formal statistical tests will be performed.

7.3 PLANNED ANALYSES

For the analysis of all primary, secondary and further endpoints, all treated patients (i.e. treated with at least one dose of trial medication) will be included in the analysis.

For the determination of MTD only MTD evaluable patients will be considered. Cohorts of patients treated with BI 836826 in combination with ibrutinib will be evaluated continuously based on the totality of the safety data available in order to determine the RP2D and MTD.

The primary analysis of all primary, secondary and further endpoints will be conducted when “last-patient-last-visit-primary-endpoint” has been reached (see [Section 8.6](#)).

7.3.1 Primary endpoint analyses

RP2D and number of patients with DLTs in first cycle, measured from first administration of BI 836826 until the end of the first cycle. The number of patients with DLTs at each dose level will be presented (all cycles and cycle 1 separately).

7.3.2 Secondary endpoint analyses

The secondary endpoint MTD will be analysed via the number of patients with DLTs during the first treatment cycle.

7.3.4 Safety analyses

Adverse events will be coded using the Medical Dictionary for Regulatory Activities (MedDRA) coding dictionary. Standard BI summary tables and listings will be produced. All AEs with an onset between start of treatment with BI 836826 and end of the REP, a period of 30 days after the last dose of BI 836826, will be assigned to the treatment period for evaluation. All treated patients will be included in the safety analysis. In general, safety analyses will be descriptive in nature and will be based on BI standards. No hypothesis testing is planned.

Statistical analysis and reporting of AEs will concentrate on treatment-emergent AEs. To this end, all AEs occurring between start of treatment with BI 836826 and end of the REP will be considered 'treatment-emergent'. The REP is defined as last administration of BI 836826 plus 30 days. Adverse events that start before first intake of BI 836826 and deteriorate under treatment will also be considered as 'treatment-emergent'. Adverse events occurring during screening and/or run-in period with ibrutinib as well as during post-treatment will be listed separately.

Analyses of AEs of all treatment cycles will be carried out under the initial treatment.

Adverse events will be graded according to CTCAE Version 4 and reported according to BI standards.

Serious Adverse Events, drug-related AEs and AESI will be tabulated. In addition, events leading to treatment discontinuation will be examined.

Frequency, severity, and causal relationship of AEs will be tabulated by system organ class and preferred term after coding according to the current version of the MedDRA.

Descriptive statistics will be used to describe changes in laboratory tests over time. In addition, all abnormalities of potential clinical significance will be reported. In general, potential clinical significance is defined as at least CTC Grade 2 and an increase in CTC

classification from baseline. Hematologic toxicity based on laboratory values will be not only described using CTCAE grading but also using the criteria described in the ‘Guidelines for the diagnosis and Treatment of CLL ([R10-4429](#)).

Vital signs, physical examinations, or other safety-relevant data observed at screening, baseline, during the course of the trial and at the end-of-trial evaluation will be assessed with regard to possible changes compared to findings before start of treatment.

7.4 INTERIM ANALYSES

No formal interim analysis is planned for this trial. Interim safety evaluations will be performed as considered necessary. Safety evaluations will be performed after each dose cohort by the SRC (for SRC details refer to [Section 3.1](#)). SRC meeting minutes and outputs provided for these SRC meetings will be documented and archived in the clinical trial master file.

7.5 HANDLING OF MISSING DATA

In general, missing data will not be imputed. Every effort will be undertaken to obtain the date of progression or response for patients known to have progressed or experienced a response and to obtain complete information on all AEs. Consequently no missing data will be imputed unless otherwise specified.

For partial or missing AE onset and/or end dates, BI internal rules will be applied for imputation.

7.6 RANDOMIZATION

No randomisation will be performed. Patients will be assigned into escalating dose cohorts by order of admission into the trial.

7.7 DETERMINATION OF SAMPLE SIZE

Approximately 20 patients will be expected for this trial. The exact number of patients within a cohort of the trial will be based on the recommendation of the SRC and the criteria specified (see [Section 7.1](#)). Based on the simulation study to evaluate operating characteristics of the BLRM (see [Section 10.7](#)), 20 patients should be a good estimate for patients to be treated in the dose escalation part for the model to have reasonable operating characteristics relating to its MTD recommendation.

8. INFORMED CONSENT, DATA PROTECTION, TRIAL RECORDS

The trial will be carried out in compliance with the protocol, the ethical principles laid down in the Declaration of Helsinki, in accordance with the ICH Harmonized Tripartite Guideline for GCP and relevant BI SOPs*.

Standard medical care (prophylactic, diagnostic and therapeutic procedures) remains in the responsibility of the treating physician of the patient.

The Investigator will inform the Sponsor immediately of any urgent safety measures taken to protect the trial patients against any immediate hazard, and also of any serious breaches of the protocol or of ICH GCP*.

The rights of the Investigator and of the Sponsor with regard to publication of the results of this trial are described in the Investigator contract.

The certificate of insurance cover is made available to the Investigator and the patients, and is stored in the ISF.

8.1 TRIAL APPROVAL, PATIENT INFORMATION, AND INFORMED CONSENT

This trial will be initiated only after all required legal documentation has been reviewed and approved by the respective IRB/ Independent Ethics Committee (IEC) and Competent Authority (CA) according to national and international regulations. The same applies for the implementation of changes introduced by amendments.

Prior to patient participation in the trial, written informed consent must be obtained from each patient (or the patient's legally accepted representative) according to ICH/GCP and to the regulatory and legal requirements of the participating country. Each signature must be personally dated by each signatory and the informed consent and any additional patient-information form retained by the Investigator as part of the trial records. A signed copy of the informed consent and any additional patient information must be given to each patient or the patient's legally accepted representative.”

The Investigator must give a full explanation to trial patients including the items listed below in association with the use of the patient information form, which is prepared avoiding the use of technical terms and expressions. The patient is given sufficient time to consider participation in the trial. The Investigator obtains written consent of the patient's own free will with the Informed Consent Form (ICF) after confirming that the patient understands the contents. The Investigator must sign (or place a seal on) and date the ICF. If a trial collaborator has given a supplementary explanation, the trial collaborator also signs (or places a seal on) and dates the informed consent.

8.2 DATA QUALITY ASSURANCE

A quality assurance audit/inspection of this trial may be conducted by the Sponsor, Sponsor's designees, or by IRB/IEC or by regulatory authorities. The quality assurance auditor will have access to all medical records, the Investigator's trial-related files and correspondence, and the informed consent documentation of this clinical trial.

8.3 RECORDS

Case Report Forms/ (e)CRF for individual patients will be provided by the Sponsor. For drug accountability, refer to [Section 4.1.8](#).

8.3.1 Source documents

Source documents provide evidence for the existence of the patient and substantiate the integrity of the data collected. Source documents are filed at the Investigator's site. Data reported on the CRF must be consistent with the source data or the discrepancies must be explained. The Investigator may need to request previous medical records or transfer records, depending on the trial; current medical records must also be available.

For the CRF, the following data need to be derived from source documents:

- Patient identification (gender, date of birth)
- Patient participation in the trial (substance, trial number, patient number, date patient was informed)
- Dates of Patient's visits, including dispensing of trial medication
- Medical/Oncology history (including trial indication and concomitant diseases, if applicable)
- medication history
- AE and outcome events (onset date (mandatory), and end date (if available))
- SAEs (onset date (mandatory), and end date (if available))
- Concomitant therapy (start date, changes)
- Originals or copies of laboratory results (in validated electronic format, if available)
- Completion of Patient's Participation in the trial"
- Prior to allocation of a patient to a treatment into a clinical trial, there must be documented evidence in the source data (e.g. medical records) that the trial participant meets all inclusion criteria and does not meet any exclusion criteria. The absence of records (either medical records or testing conducted specific for a protocol) to support inclusion/exclusion criteria does not make the patient eligible for the clinical trial.

8.3.2 Direct access to source data and documents

The Investigator/institution will permit trial-related monitoring, audits, IRB/IEC review and regulatory inspection, providing direct access to all related source data/documents. CRF/eCRF and all source documents, including progress notes and copies of laboratory and medical test results must be available at all times for review by the Sponsor's clinical trial monitor, auditor and inspection by health authorities (e.g. FDA). The (CRA) /on site monitor

and auditor may review all CRF/eCRF, and written informed consents. The accuracy of the data will be verified by reviewing the documents described in [Section 8.3.1](#).

8.4 LISTEDNESS AND EXPEDITED REPORTING OF ADVERSE EVENTS

8.4.1 Listedness

To fulfil the regulatory requirements for expedited safety reporting, the Sponsor evaluates whether a particular AE is "listed", i.e. is a known side effect of the drug or not. Therefore, a unique reference document for the evaluation of listedness needs to be provided. For BI 836826 this is the current version of the Investigator's Brochure (IB).

For ibrutinib this is the US-PI, or another regulatory label document;

The current versions of these reference documents are provided in the ISF.

8.4.2 Expedited reporting of adverse events

BI is responsible to fulfill their legal and regulatory reporting obligation in accordance with regulatory requirements. Exemptions from expedited reporting are described in [Section 5.3.7](#), if applicable..

8.5 STATEMENT OF CONFIDENTIALITY

Individual patient medical information obtained as a result of this trial is considered confidential and disclosure to third parties is prohibited with the exceptions noted below. Patient confidentiality will be ensured by using patient identification code numbers. Treatment data may be given to the patient's personal physician or to other appropriate medical personnel responsible for the patient's welfare. Data generated as a result of the trial need to be available for inspection on request by the participating physicians, the Sponsor's representatives, by the IRB/IEC and the regulatory authorities.

8.6 END OF TRIAL

The end of the trial is defined as:

- The trial is completed once the RP2D for the combination of BI 836826 with ibrutinib has been defined by the SRC (see [Section 3.1](#))

Last patient last visit (primary endpoint)

The "last-patient-last-visit-primary-endpoint" will be reached once:

- all patients have completed the REP

At this time, the CTR will be written. In case, the end of the whole trial is not reached at the time the report of the trial is being performed revised main results will be reported in a revision to the report after the end of the whole trial. There will be an additional patient contact with regard to the End of Trial status as soon as the end of the whole trial is reached.

10. APPENDICES

10.1 RAI CLASSIFICATION

Rai staging system as reported in the IWCLL guideline ([R10-4429](#)):

This system divides CLL into 5 stages:

- **Rai stage 0 (Low Risk):** Lymphocytosis in blood or bone marrow
- **Rai stage I (Intermediate Risk):** Lymphocytosis and enlarged lymph nodes.
- **Rai stage II (Intermediate Risk):** Lymphocytosis and enlarged liver or spleen with or without lymphadenopathy
- **Rai stage III (High Risk):** Lymphocytosis and anemia (Hgb <11 g/dl) with or without enlarged liver, spleen or lymph nodes
- **Rai Stage IV (High Risk):** Lymphocytosis and thrombocytopenia (platelet count <100,000/ μ l) with or without anemia or enlarged liver, spleen or lymph nodes

10.2 CRITERIA FOR RESPONSE DETERMINATION

The determination of CLL response and progression will be based on IWCLL criteria ([R10-4429](#)), including recently published clarifications and modifications ([R15-4922](#), [R15-4923](#), [R15-4921](#)) and clarifications as outlined below. In case a CR or a PD is suspected for the first time based on clinical examinations, imaging should be performed for complete response assessment.

At all protocol defined response evaluation time points, i.e. at the end of Cycle 3, Cycle 6, Cycle 9 and Cycle 12, as well as EOT, a response assessment will be performed based on CBC with differential and imaging assessment of CLL manifestations. In case a CR or a PD are suspected based on physical examination and laboratory data at any other timepoint, imaging should be obtained to confirm CR or PD. An exception is possible if unequivocal diagnosis of PD is based on criteria other than lymph node, liver or spleen size.

The ALC, neutrophil count the platelet count and hemoglobin will be used for the response assessment and all efforts should be made to obtain all parameters for response assessment on the same day. If the CBC/Differential is missing on the date of imaging, the values from a previous date as close to the imaging as possible may be used, provided that this date is 8 days or more after the last administration of BI 836826. In case ANC, PLT or hemoglobin is considered influenced by supportive therapy, e.g. growth factors, transfusions, a CR, CRi, PR, PR-L should not be based on these laboratory values. Reevaluation of blood counts should be performed as close as possible to the imaging to evaluate response. Findings on physical examination with potential impact on response assessment should be confirmed by imaging. A CBC with Differential will be performed at a central laboratory at all timepoints where MRD is assessed, and absolute lymphocyte count, absolute neutrophil count, platelet count and hemoglobin from the central laboratory should be used for disease/response assessment when available.

On imaging studies, the CLL manifestations will be classified as target lesions and non-target lesions.

Target lesions:

At baseline, up to 6 pathologically enlarged lymph nodes or lymph node masses should be selected as target lesions which will be used at each subsequent imaging for quantitative lymph node assessments during the study. Ideally, the target lesions should represent nodal disease burden due to CLL, if possible be located in disparate regions of the body, and should be reproducibly measurable in 2 perpendicular dimensions on repeated measurements. Whenever possible, mediastinal and retroperitoneal areas of disease should be considered as target lesion.

Target lesions will be measured and recorded at baseline and at all subsequent imaging time points. Bi-dimensional measurements of the Largest Diameter (LD) and the corresponding Perpendicular Diameter (PLD) will be recorded for each target lesion. The product of the LD and PLD will be calculated for each target Single Lesion Product (SLP) and the sum of the product of diameters (SPD) for all target lesions will be calculated and recorded. The baseline SPD will be used as reference for assessment of best response during treatment. The nadir LD of individual target lesions and the nadir SPD of all target lesions will be used as reference for PD.

To be considered pathologically enlarged and measurable at baseline, a lymph node must be at least 1,5 cm in short axis and measurable in two perpendicular dimensions. Smaller lymph nodes should be classified as non-target lesions if considered pathological.

At post baseline imaging time points, the LD for individual lesions and the SPD of all target lesions will be considered. Once selected, all target lesions should be measured as accurate as possible. Once a lymph node shrinks to a LD <1.5 cm, the node is considered of normal size.

Any new node considered a manifestation of CLL that measures ≥ 1.5 cm in short axis will be considered PD.

A lymph node mass may be selected as a target lesion if it is measurable at baseline. In case a lymph node mass splits into separate nodes, all separate nodes should be assessed according to the rules for single lesions and will be used in calculating the SPD. Progression of the lesion will be based on the SPD of split lesions.

Liver and spleen size:

Liver and spleen size will be measured as the Longest Cranio-Caudal Diameter (LCCD) on CT/MRI scan. The baseline and nadir values for the LCCD of liver and spleen will be used as a reference to assess tumor response. The LCCD may be directly measured on appropriate coronal or sagittal planes, or will be calculated as the product of the number of axial sections on which the organ is visualized (between the most superior and the most inferior margin) and the thickness of the sections.

The spleen will be considered enlarged if the LCCD is >12 cm ([R15-0874](#)). A LCCD decrease $\geq 50\%$ (minimum 2 cm) compared to baseline, if the spleen was enlarged at baseline, or a decrease to ≤ 12 cm is required for a spleen response. An increase in spleen LCCD by

≥50% from nadir (minimum increase of 2 cm and minimum total size of 14 cm) is required for diagnosis of splenic progression.

The liver if will be considered enlarged if it is >18 cm in LCCD ([R15-0873](#)). A LCCD decrease ≥50% (minimum 2 cm) compared to baseline, if the liver was enlarged at baseline, or a decrease to ≤18 cm is required for a liver response. Conversely, an increase in liver enlargement by ≥50% from nadir (minimum increase of 2 cm, and minimum total size of 20 cm) is required for diagnosis of liver progression.

Non-target lesions:

Any other measurable and pathological nodal lesions not selected as target lesion may be considered a non-target lesion. In addition, non-measurable evidence of CLL may be considered non-target lesion, e.g. nodal lesions too small to qualify as target lesion, extranodal lesions, bone lesions, ascites, pleural or pericardial effusions, non-measurable nodal masses.

Even if measurable, non-target lesions will not be quantitatively assessed. The persistence, unequivocal progression or complete disappearance/absence of non-target lesions should be recorded at baseline and at the subsequent imaging time points. If present at baseline, up to 6 non-target lesions should be recorded. The non-target lesions selected at baseline will be used as a general reference to further characterize regression or progression of CLL during response assessments.

Responses will be based on imaging and laboratory data, bone marrow examination needs to be added to complete response assessment for CR, and PR in some cases. Responses will be categorized as CR, CRi, PR, PR-L, SD or PD by the investigator. All data used for the assessment should be reflected in the eCRF.

Definitions of response and progression:

Complete Response (CR)

CR requires all of the following criteria to be met:

- Absolute lymphocyte count below $4 \times 10^9/L$.
- Regression of all target nodes/masses, i.e. all target lesions have a LD < 1.5 cm
- Disappearance/absence of all non-nodal non-target lesions, regression of all nodal nontarget lesions to normal sized lymph nodes
- Normal liver size (≤18 cm), based on CT imaging or non-palpable by Physical Exam
- Normal spleen size (≤12 cm), based on CT imaging or non-palpable by Physical Exam
- No evidence of new disease.
- Morphologically negative bone marrow, defined as normocellular marrow in relation to patient age, less than 30% of nucleated cells being lymphoid cells and no lymphoid nodules.
- Platelet count more than $100 \times 10^9/L$ (without exogenous growth factors or transfusion).
- Hemoglobin more than 110 g/L (without exogenous growth factors or transfusions)

- Absolute Neutrophil Count more than $1.5 \times 10^9/L$ (without exogenous growth factors).

Patients who fulfil all criteria for a CR (including a bone marrow examinations) but who have a persistent anaemia, thrombocytopenia, neutropenia or a hypocellular bone marrow related to prior or ongoing CLL therapy, but unrelated to CLL should be classified as CRi.

Partial Response (PR)

To define a PR, all of the following criteria must be met:

- No evidence of new disease
- At least one of the following laboratory criteria is present:
 - i. Platelet count higher than $100 \times 10^9/L$, or $\geq 50\%$ improvement over baseline (without exogenous growth factors or transfusion)
 - ii. Hemoglobin higher than 110 g/L, or $\geq 50\%$ improvement over baseline (without exogenous growth factors or transfusions)
 - iii. Absolute Neutrophil Count higher than $1.5 \times 10^9/L$, or $\geq 50\%$ improvement over baseline (without exogenous growth factors)
- Reduction in tumor load documented by at least two of the following criteria, with exceptions in the following situations where only 1 criterion needs to be met: (a) lymphadenopathy is the only disease manifestation (b) only lymphocytosis without lymphadenopathy is present at baseline, (c) a bone marrow assessment at screening shows quantifiable bone marrow infiltration as the only site of disease. In situation (a) only criterion (ii) will be applicable, in situation (b) only criterion (i), and in situation (c) only criterion (v).
 - i. In patients with lymphocytosis at baseline ($ALC \geq 4 \times 10^9/L$), decrease in the ALC by $\geq 50\%$ or more compared to baseline, or a decrease to $< 4 \times 10^9/L$.
 - ii. In patients with nodal disease at baseline, decrease of SPD of target lesions by $\geq 50\%$ compared to baseline.
 - iii. If spleen enlarged at baseline ($LCCD > 12$ cm), decrease of LCCD by $\geq 50\%$, or to normal size ($LCCD \leq 12$ cm).
 - iv. If liver enlarged at baseline, ($LCCD > 18$ cm), decrease of LCCD by $\geq 50\%$, or to normal size ($LCCD \leq 18$ cm).
 - v. Bone marrow infiltration of CLL decreases by $\geq 50\%$ compared to baseline, either in diffuse infiltration, or in B-lymphoid nodules.
- No target lesion and no non-target lesion (if present at baseline) are unequivocally progressing. No increase in liver and/or spleen LCCD by $\geq 50\%$

Partial Response with Lymphocytosis (PR-L)

To define a PR-L, the following criteria must be met:

- No evidence of new disease
- At least one of the following laboratory criteria is present:
 - i. Platelet count higher than $100 \times 10^9/L$, or $\geq 50\%$ improvement over baseline (without exogenous growth factors or transfusion)

- ii. Hemoglobin higher than 110 g/L, or $\geq 50\%$ improvement over baseline (without exogenous growth factors or transfusions)
- iii. Absolute Neutrophil Count higher than $1.5 \times 10^9/L$, or $\geq 50\%$ improvement over baseline (without exogenous growth factors)
- Reduction in tumor load documented by at least two of the following criteria. In patients with only one localization at baseline, improvement of this single criterion is sufficient:
 - i. In patients with nodal disease at baseline, decrease of SPD of target lesions by $\geq 50\%$ compared to baseline.
 - ii. If spleen enlarged at baseline (LCCD >12 cm), decrease of LCCD by $\geq 50\%$, or to normal size (LCCD ≤ 12 cm).
 - iii. If liver enlarged at baseline, (LCCD >18 cm), decrease of LCCD by $\geq 50\%$, or to normal size (LCCD ≤ 18 cm).
 - iv. Bone marrow infiltration of CLL decreases by $\geq 50\%$ compared to baseline, either in diffuse infiltration, or in B-lymphoid nodules.
- No PD criterion met, i.e. no target lesion and no non-target lesion (if present at baseline) are unequivocally progressing, and no increase in liver and/or spleen LCCD by $\geq 50\%$.
- Lymphocytosis during therapy with ibrutinib if occurring in isolation without other objective evidence of progressive disease will not be considered evidence of PD and will not preclude a patient from the PR-L category.

Progressive Disease (PD)

Any of the following criteria constitutes the diagnosis of PD:

- Evidence of new disease:
 - any new pathologically enlarged lymph node (>1.5 cm in short axis) considered a manifestation of CLL
 - new or recurrent increase of the liver LCCD by $\geq 50\%$, with a minimum absolute liver LCCD of 20 cm
 - new or recurrent increase of the spleen LCCD by $\geq 50\%$, with a minimum absolute spleen LCCD of 14 cm
 - any new unequivocal extranodal non-target lesion (if the non-target lesion is an effusion without additional indication for progression of CLL, there should be histological or cytological evidence that this effusion is due to CLL)
 - unequivocal reappearance of an extranodal non-target lesion that had disappeared completely on treatment
- Evidence of worsening of disease
 - SPD increase of target lesions from baseline/nadir by $\geq 50\%$
 - Increase of LD in any individual nodal target lesion from baseline/nadir by $\geq 50\%$
 - Liver progression, i.e. enlargement of the liver LCCD by $\geq 50\%$ from baseline/nadir (with a minimum increase of 2 cm and minimum total LCCD of 20 cm)
 - Spleen progression, i.e. enlargement of the spleen LCCD by $\geq 50\%$ from baseline/nadir (with a minimum increase of 2 cm and minimum total LCCD of 14 cm)

- unequivocal progression of non-target lesions overall (should not be based solely on worsening of a pleural effusion or ascites as the only location for disease progression)
- transformation into a more aggressive histology (e.g. Richter's syndrome), diagnosed by cytology or histology
- Worsening in laboratory values attributable to CLL
 - Platelet count is less than $100 \times 10^9/L$ and has decreased by $\geq 50\%$ compared to the highest platelet count on study (values obtained within one day after a transfusion should be excluded)
 - Hemoglobin is $<110 \text{ g/L}$ and has decreased by $> 20 \text{ g/L}$ from the highest hemoglobin value on study (values obtained within one day after a transfusion should be excluded)
- Lymphocytosis during therapy with ibrutinib will only be considered evidence of worsening of disease if it is not occurring in isolation, but associated with other objective evidence of progressive disease as outlined above.

Worsening of constitutional symptoms in the absence of other objective evidence of worsening of CLL will not be considered disease progression, and other causes for constitutional symptoms, e.g. infections should be considered.

Ibrutinib can mobilize CLL cells from tissues into the peripheral blood. This characteristic pharmacologic action can be prominent early in therapy, but it can also persist over time, and should not be confused with PD unless the treated patient develops other CLL-related signs or symptoms of PD. In the absence of other objective evidence of PD, lymphocytosis alone should not be considered an indicator of PD. Patients with lymphocytosis and no other evidence of PD should continue therapy until they develop other definitive signs of or the occurrence of another reason to discontinue therapy.

During therapy, anemia and/or thrombocytopenia may be difficult to differentiate from drug related effects on PLT or hemoglobin. If there is uncertainty whether there is true progression, the patient should continue study treatment and remain under close observation, e.g. with additional unscheduled assessments, which should be captured in the eCRF. If subsequent evaluations indicate CLL progression, the date of progression should be the date at which progression was first documented.

Stable Disease (SD)

For SD, the following criteria must be met:

- No evidence of new disease
- There is neither sufficient evidence of tumor shrinkage to qualify for CR/CRi/PR/PR-L nor sufficient evidence of tumor growth to qualify for definitive PD

Non Evaluable (NE)

In a patient who does not have clinical evidence for PD based on CBC/Diff, the response assessment may be NE in the following situations:

- No imaging study performed.

- Inadequate imaging quality, or missing sections which do not allow assessment of all areas in which target lesions were selected. (PD may be assigned at any timepoint regardless of the extent of missing target lesions)
- Images of liver and/or spleen missing (exception: splenectomized patient).

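### The laboratory PD limits can be met by the loss of a transfusion effect, because only values within one day of a transfusion are kept out of the on-study peak.

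*Protocol*

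**What the plan says.** Protocol Appendix 10.2, under Progressive Disease, gives two laboratory criteria headed "Worsening in laboratory values attributable to CLL".

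- Haemoglobin: below 110 g/L, with a fall of more than 20 g/L "from the highest hemoglobin value on study (values obtained within one day after a transfusion should be excluded").
- Platelets: below 100 x10^9/L, with a fall of at least 50% "compared to the highest platelet count on study (values obtained within one day after a transfusion should be excluded").

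The reference is the on-study peak, not baseline. No clause exempts a patient who is back at baseline.

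The response side of the appendix is stricter. When a count is considered "influenced by supportive therapy, e.g. growth factors, transfusions, a CR, CRi, PR, PR-L should not be based on these laboratory values". The CR definition asks for "Hemoglobin more than 110 g/L (without exogenous growth factors or transfusions"), and PR and PR-L carry the same condition for haemoglobin and platelets. None of these has a one-day limit, and the general rule does not name PD.

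After noting that cytopenia can be hard to tell from drug effects, the appendix adds: "If there is uncertainty whether there is true progression, the patient should continue study treatment and remain under close observation". Protocol section 3.3.4.1 lists PD, as assessed by the investigator, among the reasons for which a patient may be withdrawn from BI 836826.

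**The concern.** A transfused count cannot help a patient qualify for a response, but two days after the transfusion it can set the peak from which progression is measured. As the transfusion effect wears off, the count falls for a reason unrelated to disease activity, and the fall alone may be large enough. The peak never resets, so a patient who stays stable at the old baseline can go on meeting the limit at later assessments.

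The situation is foreseeable. Table 3.3.2:1 admits patients with haemoglobin from 8 g/dL (80 g/L) and platelets from 25 x10^9/L, and sections 2.3 and 4.1.4.5 provide for transfusion. In trial 1270.1 (section 1.2.1), drug-related anaemia was reported in 28% of patients and drug-related thrombocytopenia in 31%.

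A false PD would close best overall response (section 5.2.1) and supply a listed reason to withdraw a patient from BI 836826.

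**Working it through.** The plan gives no figure to reproduce, so the check applies its limits as logical tests.

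**Inputs from Appendix 10.2:** the two thresholds, the on-study peak and the one-day exclusion. **Entry limits:** Table 3.3.2:1. **Assumed, because the documents are silent:** the rise r still present more than one day after transfusion. Let b be the unchanged baseline, so that the peak is b + r and the later value is b.

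**Haemoglobin.** The limits are met if b < 110 and (b + r) - b = r > 20.

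- 80 to 101 to 80 g/L: fall 21, met.
- 80 to 100 to 80 g/L: fall 20, not met.
- Rises of 5, 10, 15 or 20 g/L do not meet the limit at any baseline tested from 80 to 110 g/L. A baseline of 110 g/L or more never meets it.

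**Platelets.** The limits are met if b < 100 and r/(b + r) >= 0.50, that is, if r >= b: the count must at least double.

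- 25 to 50 to 25: 25/50 = 50%, met.
- 25 to 45 to 25: 20/45 = 44%, not met.
- 50 to 90 to 50: 40/90 = 44%, not met.

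**With transfusion-raised values kept out of the reference,** the peak is b, the fall is 0, and neither limit is met at any baseline tested (haemoglobin 80 to 110 g/L, platelets 25 to 99 x10^9/L).

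**Adding measurement variation.** The reference is the maximum of more than 20 scheduled counts, so chance variation raises it. I simulated 40,000 stable patients per setting, with counts on the flow-chart days and PD tested at the end of Cycles 3, 6, 9 and 12. Assumed: baseline 85 g/L, within-patient SD 4 g/L, one transfusion, linear loss of its effect over 60 days. Share meeting the haemoglobin limits at least once:

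| Transfusion day | +10 g/L | +15 g/L | +20 g/L | +25 g/L |
|---|---|---|---|---|
| Day 13 | 19% | 57% | 90% | 99% |
| Day 29 | 6% | 20% | 46% | 75% |
| Day 43 | 6% | 19% | 45% | 74% |

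Without transfusion the share is 1%. If a +20 g/L transfusion is given at a transient nadir 10 to 15 g/L below baseline, it is 16% to 34%. Keeping the raised values out of the reference returns the +20 g/L rows to about 1%.

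Day 13 is close to the worst case, because the Day 15 count falls just outside the exclusion. The SD matters too: at 6 g/L the limits are met in nearly 30% of patients with no transfusion at all.

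The platelet result is more fragile. With baseline 30 x10^9/L, CV 15% and a 5-day decay (all assumed), a Day 13 transfusion adding 30 or 50 gave 32% or 89%. With linear decay and transfusion just after the Day 15, 20, 29 or 43 count, the share was about 3%, the same as without transfusion.

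**The case against.** The strongest answer is that the numeric limits are not the whole rule. The heading requires the worsening, not merely the low level, to be attributable to CLL. Loss of transfused cells with unchanged disease does not fit that description. The sentence on uncertainty is worded generally although it follows a remark about drug effects. PD is the investigator's judgement, and withdrawal is permitted rather than automatic. This stands. A reader might infer that every transfused patient who returns to baseline has PD; the documents do not support that. The simulated percentages are rates of meeting the limits, not false-PD rates, because they take attribution as always given.

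Two things limit the answer. The authors put a transfusion exclusion under that same heading, so they did not rely on attribution alone. Continued observation may also fail to settle the matter, because the peak does not reset; if progression is later accepted, it is dated back to when it was first documented.

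Two wider readings are also tempting. One is that growth factors create the same problem. Section 4.2.1.2.4 names only G-CSF, in connection with neutrophils, and neutrophils are not a PD criterion. The other is that higher dose cohorts would show more progression and so bias the RP2D. Section 1.2.1 pools cytopenia over doses and gives no transfusion rates, so there is no basis for a dose trend.

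**Conclusion.** The point holds as an inconsistency in an outcome definition. A transfusion peak can set the PD reference, and a return to an unchanged baseline can then meet the numeric limits; only investigator judgement stands between that and a false PD. Ignoring measurement variation, the rise outlasting the one-day window must exceed 20 g/L for haemoglobin or at least double the platelet count.

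How often this would happen cannot be stated from the documents. The haemoglobin range of 16% to 90% for a 20 g/L rise rests on assumed decay, variability, timing and pre-transfusion level, and should be read only as showing that the possibility is not remote.

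The consequence is modest. The endpoints are the RP2D, the number of patients with DLTs and the MTD (Protocol section 5.1; SAP sections 5.1 and 5.2.2). Overall response is one of several efficacy inputs to the RP2D (Protocol section 5.1.1), and recruitment is being stopped (section 2.1). What remains exposed is best overall response and a listed ground for withdrawal among patients still on treatment.

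**What to change.** Reconcile the two parts of Appendix 10.2 with one sentence: the highest on-study value used as the reference for laboratory PD leaves out any haemoglobin or platelet value considered influenced by transfusion. The sponsor should define how that is judged, for red cells and platelets separately.

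Leave the rule for the value being tested unchanged. Excluding transfusion-influenced test values as well could leave a regularly transfused patient with true marrow failure without an evaluable count, so that real progression is missed.

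The cost is small. Concomitant treatments and their dates are already recorded in the eCRF (Protocol section 4.2.1.2), and SAP section 7.2 already displays transfusions separately. The downside is that a few laboratory-only PDs in transfused patients may be called later.
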